- The Safety Follow-Up Visit is intended as an Exit Visit for those subjects who discontinue the trial or for those who do not continue into the Open-label Extension study following completion of Part A, Period 1 or Part A, Period 2.
- ⁷Randomization and dispensation of study drug will occur on Week 24 only for those subjects who meet criteria and will continue into Part A, Period 2.
- ³ Serum pregnancy test for females of childbearing potential only. Subjects who are surgically sterile or (hysterectomy or bilateral ligation) or post-menopausal (cessation of menses for at least 12 months prior to screening) need not be tested.
- Urine pregnancy test should be performed at the randomization visit.
- ¹⁰ Includes hematology and serum chemistry, fasted.
- ¹¹ Collect pre-dose if subject is dosing in the clinic on study visit days.
- ¹² Will include thyroid stimulating hormone and hemoglobin A1c at Screening only.
- ¹³ Includes total cholesterol, low-density lipoprotein, high-density lipoprotein, and triglycerides under fasted conditions.
- ¹⁴ If SALT score >20 at any visit in Part A, Period 2, patient will enter into Part B of the study and return to their original 8 mg BID or 12 mg BID dose from Part A, Period 1. However, all safety assessments outlined in Part A, Period 2 should be performed prior to dispensing study drug in Part B.
- ¹⁵ Dispensation in Part A, Period 2 will only occur for subjects whose SALT remains \leq 20. If SALT >20, the subject should proceed to Day 1 (Visit B1).
- ¹⁶ Day 1 (post-dose) and Weeks 12 and 24 (variable times post-dose)

Table 2: Schedule of Assessments: Part B

Event	Treatment Period									
Event	Day 1 ^{1, 2} (Visit B1)	Week 2 (Visit B2)	Week 4, 8 (Visit B3, B4)	Week 12 (Visit B5)	Week 16, 20 (Visit B6, B7)	Week 24 ³ (Visit B8)	Week 28 (Visit B-SFU)			
Physical examination						X	X			
Brief physical examination			X	X	X					
Weight			X	X	X	X	X			
Pregnancy test ⁵			X	X	X	X				
Clinical laboratory testing ⁶		X	X	X	X	X	X			
Lipid assessment ⁷				X		X	X			
12-lead electrocardiogram				X		X	X			
Vital signs			X	X	X	X	X			
SALT assessment			X	X	X	X				
Photographs			X	X	X	X				
Dispense study drug	X8		X	X	X					
Study drug accountability			X	X	X	X				
Adverse events	X									
Concomitant medications				X			X			

All subsequent visits and week increments should be based on the date of Visit B1. All visit windows are ±2 days.

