² As Day 1 occurs on the same day as the last visit from Part A, Period 2, eligible subjects for Part B will not have assessments repeated.

³ Also serves as the Early Termination Visit for patient withdrawal in this period or any patient meeting ROR criteria and entering OLE.

⁴ The Safety Follow-Up Visit is intended as an Exit Visit for those patients who do not roll over into an open-label extension and for patients who have been discontinued from the study and completed the Early Termination Visit (Week 24).

⁵ Serum pregnancy test for females of childbearing potential only. Subjects who are surgically sterile or (hysterectomy or bilateral ligation) or post-menopausal (cessation of menses for at least 12 months prior to screening) need not be tested.

⁶ Includes hematology and serum chemistry, fasted.

Includes total cholesterol, low-density lipoprotein, high-density lipoprotein, and triglycerides under fasted conditions.

⁸ Any patient from Part A, Period 2 meeting the LOM criteria will enter into Part B of the study and return to their original 8 mg BID or 12 mg BID dose from Part A, Period 1.

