receiving the 12 mg BID) or placebo. Patients in Part A, Period 2 will stay on their assigned dose for a maximum of 24 weeks or until they meet the criteria for loss of regrowth maintenance (LOM), defined as an absolute SALT score  $>20$ . Any patient meeting the LOM criteria at any assessment timepoint during Part A, Period 2 will enter Part B of the study and return to their original CTP-543 treatment from Part A, Period 1 (8 mg BID or 12 mg BID). Patients not meeting the LOM criteria (e.g., their absolute SALT score  $\leq 20$ ) at the end of 24 weeks will have the opportunity to continue receiving treatment in the Open-Label Extension study (CP543.5001) or they will complete treatment at Week 24 and return in 4 weeks for the Post-Treatment Safety Follow-up. The study design is depicted in the Study Flow Chart of the Appendix (Section 15.1).

An interim analysis to support regulatory activities related to an upcoming CTP-543 New Drug Application (NDA) submission will be conducted. The focus of the interim analyses will be on safety data and will occur following completion of Part A, Period 1. Additionally, after Part A, Period 1 completion, a PK population analysis will be completed. The PK analysis will be conducted by an outside vendor. This analysis will be described in a separate analysis plan and a separate report will be generated.

The primary efficacy assessment will be conducted when all patients have completed Part A, Period 2. An analysis of safety data will also be conducted. This analysis will be included in the NDA submission as an abbreviated report. Site personnel and patients will remain blinded to individual patient study treatments.

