#### 4. GENERAL ANALYSIS AND REPORTING CONVENTIONS

The following is a list of general analysis and reporting conventions to be applied to this study, unless otherwise specified. Departures from these general policies will be described, if applicable, in the appropriate sections of this SAP. When this situation occurs, the rules set forth in the specific section take precedence over the general policies.

All data displays (tables, listings, and figures) will have a header showing the sponsor company name, protocol number, page number, and display status (i.e. “DRAFT” or “FINAL”), as well as a footer indicating file name and run date/time. Summary tables and data listings will be summarized by treatment group for efficacy and exposure, and by treatment group and overall otherwise. All data for analysis may be listed by-patient.

Specifically, for each Part and Period of the study, the summary table layout will be as follows:

For Part A, Period 1 tables:

Treatment Phase		
CTP-543 8 mg BID	CTP-543 12 mg BID	Total

For Part A, Period 2 tables:

Dose Reduction		Drug Discontinuation		Total
CTP-543 8 mg BID to 4 mg BID	CTP-543 12 mg BID to 8 mg BID	CTP-543 8 mg BID to Placebo	CTP-543 12 mg BID to Placebo	

For Part B tables:

Dose Reduction		Drug Discontinuation		Total
CTP-543 8 mg BID to 4mg BID to 8 mg BID	CTP-543 12 mg BID to 8 mg BID to 12 mg BID	CTP-543 8mg BID to Placebo to 8 mg BID	CTP-543 12 mg BID to Placebo to 12 mg BID	

Note that for all efficacy and exposure tables, the total column will not be displayed.

Categorical variables will be summarized using counts (n) and percentages (%) and will be presented in the form “n (xx.x).” If a count is 0, no percentage will be shown. If a percentage is 100%, 100 will be shown. To ensure completeness, summaries for categorical variables will include all categories, even if no patients had a response in a particular category. Unless otherwise specified, the denominator for each percentage will be based on the number of patients in the population being summarized (header n). Percentages will be rounded to one decimal place.

Continuous variables will be summarized using mean, standard deviation, minimum, maximum, median, and number of patients. The minimum and maximum will be the same precision as the

Concert Pharmaceuticals, Inc.  
Statistical Analysis Plan – CP543.2004

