#### 8.1.2. Assessment Time Windows

The visit schedule for all study assessments is provided in Appendix 15.2, by Part. For scheduled visits, there will be no reassignment of the analysis visit based on date. Unscheduled visits and early termination visits will be reassigned based on the analysis windows in the below table and the schedule of events. Assessments in part B will be windowed counting from the part B treatment start date. Assessments may only be re-assigned to visits where they were to be collected per the schedule of events. The latest assessment in a window will be selected as the visit used in summaries, unless otherwise specified. All visits will be included in by-patient data listings.

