## **8.4. Secondary Endpoints**

Analyses for secondary endpoints will be performed using the Efficacy Population.

Missing values will not be imputed.

Concert Pharmaceuticals, Inc.  
Statistical Analysis Plan – CP543.2004

For the secondary endpoints of proportions or percentages of patients achieving specified improvement criteria (hereinafter, “secondary responder endpoints”), pairwise treatment group differences in percentages and 95% CIs will be calculated in Part A Period 1 only.

Observed counts and percentages of responders will be summarized by treatment group for each Part/Period. 95% confidence intervals for percentages of responders and/or non-responders will be calculated using the binomial approximation with a Wald continuity correction.

For the secondary endpoints of absolute or relative changes (hereinafter, “continuous secondary endpoints”), continuous secondary endpoints will be summarized with descriptive statistics only and no treatment differences will be calculated. Descriptive statistics will include the number of subjects with data, mean, standard deviation, median, minimum, and maximum.

For Part A Period 1 only, treatment differences for continuous secondary endpoints will be assessed with a mixed-effect model of repeated measures (MMRM). Baseline SALT score will be included as a model covariate. Treatment group comparisons at each visit will be based on least squares (LS) mean estimates. An unstructured covariance matrix will be used to model the within-subject errors. Should the model fail to converge, an alternative autoregressive covariance matrix will be used instead. The Kenward-Roger approximation will be used to estimate the denominator degrees of freedom. Assuming that the data are MAR, the estimates of the treatment differences calculated from the MMRM described above are unbiased. Standard descriptive statistics will be reported for each time point on the values and changes from baseline along with the LS means, standard errors, 95% CIs and differences between treatment groups reported with LS means, standard errors, and 95% CIs. P-values will not be displayed.

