#### 8.4.1. Secondary SALT Endpoints

The following secondary SALT responder endpoints will be assessed:

Part A

- Percentage of patients achieving LOM criteria (SALT > 20) for each *dose reduction* condition at Weeks 4, 8, 12, 16, 20, and 24 (Period 2 ONLY). Note that these timepoints in Period 2 are equivalent to Weeks 28, 32, 36, 40, 44, and 48, respectively.
- Percentage of patients achieving LOM criteria (SALT > 20) for each *drug discontinuation* condition at Weeks 4, 8, 12, 16, 20, and 24 (Period 2 ONLY). Note that these timepoints in Period 2 are equivalent to Weeks 28, 32, 36, 40, 44, and 48, respectively.
- Percentage of patients achieving an absolute SALT score  $\leq 20$  at Weeks 4, 8, 12, 16, 20, and 24 (Period 1 ONLY)
- Relative change in SALT scores from Baseline at Weeks 4, 8, 12, 16, 20, and 24 (Period 1 ONLY)

Part B:

- Percentage of patients achieving the ROR criteria (SALT  $\leq 20$ ) at Weeks 4, 8, 12, 16, and 20
- Relative change in SALT scores from Part B Baseline at Weeks 4, 8, 12, 16, 20, and 24

Concert Pharmaceuticals, Inc.  
Statistical Analysis Plan – CP543.2004

Secondary endpoints on percentage of patients achieving an absolute SALT score of  $\leq 20$  or SALT  $> 20$ , will be assessed according to Section 8.4.

The continuous secondary SALT endpoint of relative change in SALT score from baseline at Weeks 4, 8, 12, 16, 20, and 24 in Part A Period 1 will be assessed with an MMRM, according to Section 8.4. The baseline SALT score will be as follows for each endpoint per Part:

Relative reduction is based on relative change from baseline.

Relative change in SALT score is derived as percent change of the follow-up SALT score, where baseline SALT score is the denominator (i.e. absolute change divided by the baseline score, multiplied by 100).

In addition, summary statistics for the mean, mean change, and mean relative change in total SALT score from Part A Period 1 baseline will be reported for Part A Period 1, Part A Period 2, and Part B. The mean and mean change in total SALT score from Part A Period 2 baseline will be reported for Part A Period 2 and Part B. Mean relative change from Part A Period 2 baseline will not be calculated as baseline values may be zero by design and would result in undefined relative changes. The mean, mean change, and mean relative change in total SALT score from Part B baseline will be reported for Part B.

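### By-visit Period 2 LOM is not defined as cumulative, so the LOM row of Table 14.2.2.2 and Figure 14.2.2.1.2 can fall while cumulative loss rises

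*SAP*

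**What the plan says.** SAP 8.4.1 lists, for each dose reduction and each drug discontinuation condition, the percentage of patients achieving LOM at Weeks 4, 8, 12, 16, 20 and 24 of Period 2. It sends "Secondary endpoints on percentage of patients achieving an absolute SALT score of" 20 or less, or above 20, to SAP 8.4. That section states "Observed counts and percentages of responders will be summarized by treatment group for each Part/Period" and "Missing values will not be imputed". It names no denominator, so the default in SAP section 4 applies: "the denominator for each percentage will be based on the number of patients in the population being summarized (header n".

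The design removes LOM patients from Period 2. SAP section 3 says "Any patient meeting the LOM criteria at any assessment timepoint during Part A, Period 2 will enter Part B of the study". Protocol Table 1, footnote 15, sends a patient with SALT above 20 straight to Visit B1. Protocol Table 2, footnote 2, explains why nothing is repeated there: "As Day 1 occurs on the same day as the last visit from Part A, Period 2". From then on, by SAP 8.1.2, "Assessments in part B will be windowed counting from the part B treatment start date".

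The results go into Table 14.2.2.2 (LOM and Response by visit), Figure 14.2.2.1.2 (LOM alone over time) and Figure 14.2.2.1.3 (SALT ≤20 over time). SAP 15.4 marks all three for the abbreviated NDA report.

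**The concern.** A LOM patient has no Period 2 SALT score after the LOM visit. No rule in 8.4 or 8.4.1 keeps that patient counted as LOM at later visits, and the no-imputation rule points the other way. Taken literally, the LOM entry at Week 16 is LOM found at Week 16 and not LOM reached by Week 16.

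The trial has no hypothesis tests, so its descriptive displays are its results, and loss after dose reduction or discontinuation is its primary objective. A LOM curve that peaks and then declines looks like stabilisation when it may only show that few patients are left to lose hair. Two arms can also appear in the wrong order, because the arm with heavier early loss has fewer patients remaining at Week 24. Figure 14.2.2.1.2 is the most exposed display, since it has no Response row beside it.

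**Working it through.** **Inputs.** The planned arm size is about 25: SAP 7.2 expects about 50 Responders per dose group, randomized 1:1, and 50/2 = 25. There is no power or alpha figure to reproduce. The documents give no Period 2 LOM rates (Protocol 5.2.1 says there are no discontinuation data for CTP-543), so every LOM pattern below is an assumption.

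**Illustration.** 25 patients, no dropout, new LOM 2, 5, 5, 4, 2, 1. LOM row = new LOM / 25. Cumulative = sum of new LOM to date / 25. SALT ≤20 row = (patients in Period 2 at the visit − new LOM) / 25.

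| Week | In Period 2 | New LOM | LOM row | Cumulative LOM | SALT ≤20 row |
|---|---|---|---|---|---|
| 4 | 25 | 2 | 8% | 8% | 92% |
| 8 | 23 | 5 | 20% | 28% | 72% |
| 12 | 18 | 5 | 20% | 48% | 52% |
| 16 | 13 | 4 | 16% | 64% | 36% |
| 20 | 9 | 2 | 8% | 72% | 28% |
| 24 | 7 | 1 | 4% | 76% | 24% |

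At Week 24 the two printed rows sum to 4 + 24 = 28%. The other 18/25 = 72% had LOM at an earlier visit and are in neither row. The planned interval, p ± (1.96·√(p(1−p)/n) + 1/(2n)), is −5.7 to 13.7% for 1/25 and 57.3 to 94.7% for 19/25. One report could therefore show 4% for Week 24 LOM and 76% for primary LOM in the same arm.

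**Other assumed patterns, n = 25.** With new LOM 2, 6, 5, 3, 1, 1, the LOM row falls from 24% (Week 8) to 4% (Week 20) while cumulative LOM rises from 32% to 68%. With 1, 2, 2, 1, 1, 0, it falls from 8% (Week 12) to 4% (Week 20) while cumulative LOM rises from 20% to 28%. If patients assessed at the visit were the denominator, the first of these patterns would still fall, from 5/17 = 29.4% (Week 12) to 1/9 = 11.1% (Week 20).

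**Constant hazard.** Let q be the true 24-week LOM and h = 1 − (1−q)^(1/6) the risk per visit. The header-n Week 24 entry is h(1−h)^5.

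- q = 20%: h = 0.0365, entry 3.0%
- q = 50%: h = 0.1091, entry 6.1%
- q = 80%: h = 0.2353, entry 6.2%
- q = 90%: h = 0.3187, entry 4.7%

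The maximum is at h = 1/6: (1/6)(5/6)^5 = 6.7%. An arm with 90% loss would plot below an arm with 50% loss. This ceiling belongs to constant hazard only. If all 19 losses of the illustration were first seen at Week 24, the entry would be 19/25 = 76% and correct.

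**Dropout.** Keep the 19 LOM patients, but let 2 of the 6 maintained patients leave after Week 12 without LOM and 1 miss Week 24. The SALT ≤20 row reads 3/25 = 12%, and its complement is 88% against observed LOM of 76%. The complement therefore mixes LOM with dropout and missed visits. One minus Kaplan-Meier, with 25, 23, 18, 11, 7 and 4 at risk, is 1 − (13/25)(5/11)(3/4) = 82.3%.

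**Rounding (separate, minor).** SAP section 4 says that movement between parts used SALT rounded to an integer, while analysis uses unrounded SALT. With the weights in Protocol 18.2, quadrant losses of 10 (left), 10 (right), 30 (top) and 20 (back) give 1.8 + 1.8 + 12.0 + 4.8 = 20.4. That rounds to 20, so the patient stays in Period 2, yet is analysed as LOM. If the top quadrant later falls to 25, the total is 18.4: Kaplan-Meier (first value above 20) records LOM and the primary (last value) records maintenance. Each such patient is 1/25 = 4 points. How often this occurs is unknown.

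**The case against.** The strongest reply is that the endpoint is unclear and not wrong. Achieving LOM at a given week can mean LOM reached by that week, and new LOM per visit is itself a legitimate statistic if so labelled. SAP section 4 refers to mock tables that are not in the public documents, and a row label or footnote there could settle the matter. This stands in part: the wording does not wholly exclude a cumulative reading. But observed counts without imputation favour the at-visit reading, and two programmers could produce different tables from the same text.

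The second reply is that sound displays are already planned. The primary uses the last observed Period 2 score (8.2.1), and 8.5.1 gives Kaplan-Meier time to first LOM with a plot. Both are in the abbreviated report. The disposition category for LOM, the missing-SALT summary and the SALT-over-time listing also carry the loss. This stands, and it limits the point to one row and one figure.

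A reader might infer that maintained response is overstated too. The documents do not support that: with the default header n, the SALT ≤20 row is the correct maintained proportion when nobody drops out. Only patients assessed at the visit as denominator would inflate it (6/7 = 86% against 24% at Week 24 of the illustration), and the SAP does not name that denominator.

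**Conclusion.** The point holds as a defect in the definition of a secondary display. Following 8.4 literally gives a by-visit LOM series that can decline while loss accumulates, and it can rank arms wrongly at late visits. The illustrated size, 4% against 76% at Week 24, rests on assumed counts. The direction needs only that new losses become fewer at later visits, and with late loss the row need not fall. The primary analysis, Kaplan-Meier and the header-n SALT ≤20 row are not affected by this gap, and no test depends on it.

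Two stronger readings should be avoided. The 6.7% ceiling is not general; it needs constant hazard. Nor would using rounded SALT guarantee that cumulative LOM at Week 24 equals the primary LOM count. Protocol 9.3 keeps patients who stop study drug in follow-up with efficacy assessments. Such a patient may remain in Period 2 after a score above 20, and the documents do not say that all of them enter Part B.

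**What to change.** In SAP 8.4.1:

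- Define by-visit LOM as first LOM in Period 2 at or before the visit, over all Efficacy Population patients who entered that Period 2 arm.
- Define Response as SALT ≤20 at the visit with no earlier LOM, with the same denominator.
- Add a row for patients who left or were not assessed without LOM, so that the rows sum to 100%. In the dropout example, Week 24 becomes LOM 76%, Response 12%, left or not assessed 12%.
- Label any at-visit count as newly observed LOM, and refer to the 8.5.1 Kaplan-Meier analysis as the dropout-adjusted time course.

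Cost: a few sentences and minor reprogramming of Table 14.2.2.2 and Figures 14.2.2.1.2 and 14.2.2.1.3. The by-visit LOM percentages become less favourable.

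Separately, state one SALT precision for LOM in the by-visit, primary and Kaplan-Meier analyses, and show the other as a sensitivity analysis. This costs more, because a change of precision touches the primary and Kaplan-Meier outputs and adds a sensitivity version.

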#### Part A

##### Period 1

Patients will be screened up to 28 days prior to initiation of study drug. Patients will provide appropriately-obtained informed consent prior to initiating any screening procedures. Patients meeting initial screening criteria will be eligible to continue to the Day 1 (Baseline) visit for review of eligibility and baseline assessments, including SALT assessment, physical examination, clinical laboratory assessments, electrocardiograms (ECGs) and vital signs. Patients meeting all inclusion criteria and none of the exclusion criteria are eligible to enter Part A, Period 1 of the study.

Part A, Period 1 is a double-blind Treatment Period where patients will be randomized to receive either 8 mg BID or 12 mg BID CTP-543 for 24-weeks. Randomization will be stratified by scalp hair loss into one of the following two categories: 1) Partial scalp hair loss (SALT  $\geq 50$  and  $<95$ ); 2) complete or near-complete scalp hair loss (SALT  $\geq 95$ ). Patients will take the first dose of study drug in the clinic on Day 1 and will be instructed to take study drug daily approximately every 12 hours for the duration of Period 1. Other baseline assessments for Part A, Period 1 will include Patient and Clinician Global Impression of disease Severity (CGI-S and PGI-S), and Patient Reported Outcome for Satisfaction (SPRO) and Hair Quality (QPRO). Blood samples for pharmacokinetic assessment will be taken periodically. At End of Treatment (EOT) for Part A, Period 1, treatment success (Responders) will be defined as patients from each dose group having an absolute SALT score of  $\leq 20$  at Week 24. These Responders will enter Part A, Period 2 of the study. Patients having an absolute SALT score  $> 20$  will be defined as a Non-Responder and will have the opportunity to continue receiving treatment in the Open-Label Extension study (CP543.5001) or they will complete treatment at Week 24 and return in 4 weeks for the Post-Treatment Safety Follow-up.

##### Period 2

In Part A, Period 2, patients will be re-randomized to receive either a lower dose of CTP-543 (4 mg BID for patients previously receiving 8 mg BID or 8 mg BID for patients previously

Concert Pharmaceuticals, Inc.  
Statistical Analysis Plan – CP543.2004

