### 7.2. Randomization

#### Part A Period 1

Patients will be randomized such that approximately N = 130 for 12 mg BID and N = 170 for 8 mg BID in an attempt to have approximately equal numbers of patients eligible for Part A, Period 2. Randomization will be stratified by scalp hair loss into one of the following two categories: 1) Partial scalp hair loss (SALT  $\geq$  50 and  $<$  95); 2) Complete or near-complete scalp hair loss (SALT  $\geq$  95).

The randomization schedule will be generated prior to study start. Tablets and packaging of 8 mg and 12 mg CTP-543 will be identical in appearance.

#### Part A Period 2

For each dose group, patients identified as Responders in Period 1 will be randomized in a 1:1 ratio to a dose reduction arm or a placebo (drug discontinuation) arm. For the dose reduction arm, patients previously on 12 mg BID in Period 1 will be assigned to 8 mg BID and patients previously on 8 mg BID will be assigned to 4 mg BID. Given the previous experience with the primary endpoint for Period 1, it is expected that approximately 50 patients from each dose group in Period 1 will be Responders. Consequently, it is expected that approximately 25 patients from each dose group will be assigned to dose reduction and 25 patients will be assigned to drug discontinuation in Period 2.

The randomization schedule will be generated at the end of Period 1. Tablets and packaging for 4 mg CTP-543, 8 mg CTP-543 and placebo will be identical in appearance.

Part B

For each dose group, patients identified as having a LOM following either *dose reduction* or *drug discontinuation* in Part A, Period 2 will be assigned back to the original dose they received in Part A, Period 1. Study drug dosing regimen will be blinded by administering 2 x 8 mg tablets or 2 x 12 mg tablets twice-daily for 24 weeks. Tablets and packaging of 8 mg and 12 mg CTP-543 will be identical in appearance.

A by-patient listing of randomized treatment group and randomization number will be presented for each Part/Period.

All study patients, Investigators, and site study staff will be blinded to study drug assignment for the duration of the study.

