#### **8.4.4. Clinical Global Impression of Severity (CGI-S)**

The CGI-S will be assessed by the Investigator and will consider the severity of the patient's alopecia areata at the time of assessment. The Investigator may select one of seven numeric choices representing "Among the most extreme hair loss" to "Normal, no hair loss". To reduce variability, one rater should perform the CGI-S assessment for the patient for the duration of the study. An example of the CGI-S assessment can be found in Appendix 18.3.1 of the protocol.

The continuous secondary endpoint of change from baseline in the CGI-S at Weeks 12, 16, 20, and 24 will be assessed per Section [8.4](#) in Part A Period 1 only. No missing data will be imputed for this endpoint.

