#### **8.4.6. Patient Global Impression of Severity (PGI-S)**

The PGI-S will be assessed by the patient and will consider the severity of his/her alopecia areata at the time of assessment. The patient may select one of seven numeric choices representing "Among the most extreme hair loss" to "Normal, no hair loss". An example of the PGI-S assessment can be found in Appendix 18.3.3 of the protocol.

The continuous secondary endpoint of change from baseline in the PGI-S at Weeks 12, 16, 20, and 24 will be assessed per Section [8.4](#) in Part A Period 1 only. No missing data will be imputed for this endpoint.

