#### **8.4.7. Quality of Hair Patient Reported Outcome (QPRO)**

The QPRO questionnaire is a 4-item assessment which provides additional details on key attributes of patient hair and helps provide context to the SPRO response. Like the SPRO, the QPRO responses are on a scale of 1-5, where 1 = very satisfied, 2 = satisfied, 3 = neither satisfied nor dissatisfied, 4 = dissatisfied, and 5 = very dissatisfied. An example of the QPRO assessment can be found in Appendix 18.4.2 of the protocol.

The continuous secondary endpoints of change from baseline for each individual item of QPRO at Weeks 12, 16, 20, and 24 will be assessed per Section [8.4](#) in Part A Period 1 only. No missing data will be imputed for this endpoint.

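### The MMRM for CGI-S, PGI-S and the QPRO items adjusts for baseline SALT but not for the endpoint's own baseline, which generally costs precision

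*SAP*

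**What the plan says.** SAP 8.4 (Secondary Endpoints) specifies an MMRM for treatment differences on the continuous secondary endpoints, for Part A Period 1 only. The one covariate it names is baseline SALT: "Baseline SALT score will be included as a model covariate". It reports LS mean differences with standard errors and 95% CIs, and no p-values.

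Three later subsections send their endpoints to that model and add no covariate:

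- SAP 8.4.4: "The continuous secondary endpoint of change from baseline in the CGI-S at Weeks 12, 16, 20" and Week 24.
- SAP 8.4.6: "The continuous secondary endpoint of change from baseline in the PGI-S at Weeks 12, 16, 20" and Week 24.
- SAP 8.4.7: "The continuous secondary endpoints of change from baseline for each individual item of QPRO", of which there are four.

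The matching baselines are available. The SAP's Part A summary states: "Other baseline assessments for Part A, Period 1 will include Patient and Clinician Global Impression of disease Severity", and the same sentence adds SPRO and QPRO. The schedule of assessments places all of them on Day 1.

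On balance at entry, the SAP says "Randomization will be stratified by scalp hair loss into one of the following two categories", both defined by SALT. No other baseline is a stratification factor. Neither SAP 13 nor the protocol adds an own-baseline term.

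**The concern.** Of the seven continuous endpoints under this model, baseline SALT is the outcome's own baseline for only one, relative change in SALT. For the other six it is the baseline of a different scale.

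Change on a bounded scale depends on where the patient starts. A patient who answers 1 on a QPRO item cannot improve, while one who answers 5 can improve by four points. The same holds for the seven-point severity scales. Leaving the own baseline out has two consequences. A chance difference between dose groups on that baseline is carried in part into the estimated dose difference. Variation that the own baseline could explain also stays in the residual and widens the interval.

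The estimate and its 95% CI are all the reader gets for these contrasts, because no p-values are shown. Tables 14.2.3.4 to 14.2.3.6, which hold these results, are marked in SAP 15.4 for the abbreviated report supporting the NDA.

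**Working it through.** The plan states no SD, correlation or interval width for these endpoints, so it has no figure of its own to reproduce.

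**Inputs from the documents.** Planned group sizes are "approximately N = 130 for 12 mg BID and N = 170 for 8 mg BID" (SAP 7.2).

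**Assumed inputs.** Scale the own baseline to SD 1.
- k = follow-up SD divided by baseline SD: 1, 1.5 or 2.
- ρ = correlation of own baseline with follow-up: 0.2 to 0.6.
- r = correlation of baseline SALT with own baseline: 0.4 to 0.7.
- Correlation of baseline SALT with follow-up = r × ρ, so SALT predicts follow-up only through the own baseline.

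With complete data and covariate-by-visit terms, the MMRM contrast at one visit behaves like an ANCOVA of the change score, so residual variances can be compared directly.

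**Step 1: precision.** The variance of the change is k² + 1 − 2kρ, which equals k²(1 − ρ²) + (1 − kρ)². Adjusting for SALT removes r²(1 − kρ)². Hence:

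- SALT only: V₁ = k²(1 − ρ²) + (1 − r²)(1 − kρ)²
- SALT plus own baseline: V₂ = k²(1 − ρ²)
- Interval narrowing = 1 − √(V₂/V₁)

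| k | ρ = 0.2, r = 0.4 | ρ = 0.6, r = 0.7 |
|---|---|---|
| 1 | 0.96/1.4976 = 0.641; 20% narrower | 0.64/0.7216 = 0.887; 6% narrower |
| 1.5 | 2.16/2.5716 = 0.840; 8% narrower | 1.44/1.4451 = 0.996; 0.2% narrower |
| 2 | 3.84/4.1424 = 0.927; 4% narrower | 2.56/2.5804 = 0.992; 0.4% narrower |

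The gain is zero when the slope on the own baseline, kρ, equals 1. At k = 2 this happens at ρ = 0.5, inside the assumed range.

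**Step 2: relaxing the product assumption, at k = 1.** Let s be the SALT-to-follow-up correlation, from 0.2 to 0.4. Then V₁ = 2(1 − ρ) − (s − r)² and V₂ = 1 − (ρ² + s² − 2ρsr)/(1 − r²).
- s = 0.4, ρ = 0.2, r = 0.4: 0.838/1.600 = 0.524; 28% narrower.
- s = 0.2, ρ = 0.6, r = 0.7: 0.545/0.550 = 0.991; 0.4% narrower.

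**Step 3: chance imbalance.** The 95% range of the baseline mean difference is ±1.96 × √(1/170 + 1/130) = ±0.228 baseline SD. Under the product assumption, SALT-only adjustment leaves (1 − kρ) × √(1 − r²) × 0.228 in the estimate at the edge of that range:
- k = 1: 0.8 × 0.917 × 0.228 = 0.17 SD at ρ = 0.2, r = 0.4; 0.4 × 0.714 × 0.228 = 0.07 SD at ρ = 0.6, r = 0.7.
- k = 1.5: 0.7 × 0.917 × 0.228 = 0.15 SD and 0.1 × 0.714 × 0.228 = 0.02 SD.

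**Step 4: check by simulation.** I used one scenario (k = 1, ρ = 0.5, r = 0.3) with 5,000 runs. The formulas give SE = √0.9775 × 0.1165 = 0.115 with SALT only and √0.75 × 0.1165 = 0.101 with the own baseline added. The mean simulated SEs were 0.115 and 0.101. Neither estimator was biased on average. The correlation of the estimate with the observed baseline imbalance was −0.49 with SALT only and −0.03 with the own baseline added.

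**The case against.** The strongest objection concerns size. The 6% to 20% gain needs equal SDs at baseline and follow-up, which is the favourable case. Entry requires SALT of at least 50, which may compress baseline severity. By Week 24 the groups are expected to split: Protocol 13.1 anticipates about 50 responders among 170 patients (29%) and 50 among 130 (38%). Follow-up spread may well exceed baseline spread, and the gain then shrinks towards zero. This stands, although the documents give no SDs to settle it. It applies least clearly to the eyebrow and eyelash items, since no entry criterion restricts them.

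The second objection is consequence. The study is descriptive, SAP 8.3 names no key secondary endpoints, and no decision rule uses these intervals. This also stands.

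A reader might infer more than the documents support:
- **Bias.** Dose is randomized, so omitting a baseline covariate does not bias the estimate over repeated randomization. The intervals are inefficient, not invalid.
- **The own baseline as the strongest predictor of change.** This is plausible, but the documents report no correlations.
- **Scalp SALT as irrelevant to eyebrows and eyelashes.** Protocol 5.1 describes disease of the scalp or of scalp and body hair, including universalis. A weaker link is plausible; no link is not shown.

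**Conclusion.** The concern holds as a modest efficiency point. As written, the SAP adjusts six of its seven continuous Period 1 endpoints for another scale's baseline and not for their own. Unbiasedness over repeated randomization is not in question. What is lost is protection against imbalance in the trial actually run, and some precision.

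Under the product assumption, the own baseline narrows intervals by about 6% to 20% with equal SDs and by about 0% to 8% with a follow-up SD 1.5 to 2 times larger. With equal SDs but that assumption relaxed, the range is about 0.4% to 28%. No single figure can be defended from the documents. The direction can: in large samples the added covariate does not widen the interval, and it leaves the width unchanged only when the own-baseline slope is 1. The co-primary Period 2 results, the Part B results, the time-to-LOM analysis and the SALT model are untouched.

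**What to change.** In SAP 8.4, state that each MMRM for CGI-S, PGI-S and the individual QPRO items includes the endpoint's own Part A Period 1 baseline and its interaction with visit, with baseline SALT kept as a second covariate. Leave the model for relative change in SALT as it is, since baseline SALT is already its own baseline.

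The cost is one SAP sentence, the matching programming change in six models and a few degrees of freedom. No new data are needed. No patient is lost, because a change score already requires the own baseline.
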